### 5.1.1.2 Study Periods

The maximum study duration per study participant will be 37 weeks.

- Screening Period (Day -42 to Day -15): Eligibility will be assessed during the Screening Period of up to 28 days
- Run-In Period (Day -14 to Day -1): Study participants who have been confirmed eligible to participate in the study will be randomized 1:1:1 to study treatment. During the 2-week Run-In Period, all study participants will receive placebo sc QW and will be blinded to this treatment.

---

- Treatment Period 1 (Day 1 to Day 84): Study participants will receive their randomized treatments for the first 12-week Treatment Period.
- Treatment Period 2 (Day 85 to Day 168): Study participants will receive their randomized treatments for the second 12-week Treatment Period.
- Run-Out Period (Day 169 to Day 182): At the end of both 12-week Treatment Periods, all study participants will receive placebo sc QW during a 2-week Run-Out Period and will be blinded to this treatment.
- Safety Follow-up Period (SFU, Day 183 to Day 218): Study participants who complete both Treatment Periods and Run-Out Period will enter the 5-week SFU Period.
- Study participants who permanently discontinue IMP are encouraged to complete the EOT/EW Visit and the SFU/End of Study (EOS) Visit. In these cases, the SFU will not take place between study Day 183 to Day 218.
- Safety analysis will include periods from Run-In through end of SFU period. Efficacy, PK and PD analysis will include data collected from Treatment Period 1 to end of SFU Period.

Efficacy, PK and PD measurements collected post-Baseline and up to and including Visit 15 will be allocated to Treatment Period 1. Efficacy, PK and PD measurements collected after Visit 15 and up to and including Visit 27 will be allocated to Treatment Period 2.

For the purposes of analysis, data including AEs, IPDs, and medications will be assigned a study period using the rules summarized in Appendix 4 [Section 8.4](#).

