**Table 5-2: Definition of Baseline**

Endpoint	Definition of Baseline
Hematology, serum chemistry, urinalysis, vital signs	Baseline is defined as the most recent value obtained prior to the first dose of IMP in the Run-In Period, or Screening if this is missing.
Efficacy	
Baseline is defined as the measurements on Day 1 (Visit 3, Week 1) prior to administration of treatment or during Run-In Period depending on the endpoint:
 
 
For BPI-SF, the Baseline measurement is at Day 1 (Visit 3, Week 1). If Day 1 measurement is missing, then the Screening measurement will be used.
 
For Pain NRS, and Fatigue NRS, the Baseline measurement will be the average of the 7 days prior to Day 1 (Visit 3, Week 1), not including Day 1 data. If there are <3 assessments available within the 7 days, the Baseline measurement will be missing.
 
For FIQR, the Baseline will be the last assessment before Day 1. This is Day -7 (Visit 2, Week -1) or Screening visit if Day-7 is missing.
 
 
Note that for all endpoints listed above, if a dose of study medication was not received at Visit 3, but the efficacy assessment was performed at Visit 3 (or Visit 2 for FIQR), the Baseline assessment would be defined as above.

Pharmacodynamics (PD)	
Baseline is defined as the latest non-missing assessment performed prior to dosing on Day 1 (Visit 3, Week 1). If Day 1 measurement is missing, the Run-In (Visit 1, Week -2) measurement will be used.
 
Note that if a dose of study medication was not received at Visit 3, but the PD assessment was performed at Visit 3, this would still be used as the Baseline assessment.

Pressure Pain Threshold	
Baseline is defined as the average of the three assessments performed per site, prior to dosing on Day 1 (Visit 3, Week 1).
 
Note that if a dose of study medication was not received at Visit 3, but the Pressure Pain Threshold assessment was performed at Visit 3, this assessment would still be used as the Baseline assessment.

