Anti-drug antibody (ADA)	
Baseline is defined as the last measurement prior to receiving the first dose of rozanolixizumab. For participants randomized to Sequence 1, Baseline is the Day 1 (Visit 3, Week 1) pre-dose assessment, or Day -7 (Visit 1, Week -1), if missing. For participants randomized to Sequence 2, Baseline is the Day 85 (Visit 15, Week 13) pre-dose assessment, or Day 1 (Week 3, Visit 1), if missing.
 
Note that if a dose of study medication was not received at Visit 3, or Visit 15 (dependent upon the participant), but the ADA assessment was performed at Visit 3 or Visit 15, this assessment would still be used as the Baseline assessment.

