**Table 5-4: Sequence Descriptions**

Sequences	Full Description	Data Display Description
1	Sequence 1: Rozanolixizumab 12 weeks in Treatment Period 1, rozanolixizumab 12 weeks in Treatment Period 2	Seq1: RLZ 12w +RLZ 12w
2	Sequence 2: Placebo in Treatment Period 1, rozanolixizumab 12 weeks in Treatment Period 2	Seq2: PBO+RLZ 12w
3	Sequence 3: Placebo in Treatment Period 1 and Treatment Period 2	Seq3: PBO+PBO

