For correlation analysis between clinical endpoints and PD data, scatterplots including regression lines and Pearson correlation coefficients will be provided for change and percent change from Baseline at Visit 15 (or Visit 27) in total IgG versus:

- Change from Baseline at Visit 15 and Visit 27 in BPI-SF interference.
- Change from Baseline at Visit 13 and Visit 25 for FIQR
- Change from Baseline based on the average score at Visit 14 and Visit 26 and the following 6 days, for pain NRS and fatigue NRS.

Scatterplots will be summarized by treatment group.

Boxplots of maximum change and percent change from Baseline for Total IgG will also be plotted by sequence and period, for a total of 6 box plots.

All pharmacodynamic summaries and figures will be presented based on the PDS, and listings will be presented using the SS-r.

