- The first occurrence of treatment-emergent ADA positivity: cumulative number and percentage of TE-ADA positive participants (category 7) who are ADA positive for the first time based on samples collected over the entire study duration, including SFU.
- Summary table of mean maximum percentage change from Baseline in total IgG summarized by ADA participant categories (1-6) for the following:
  - Sequence 1, Treatment Period 1 (RLZ 12 weeks) using ADA participant category based on RLZ 12 weeks exposure and maximum percent change from Baseline in total IgG in Treatment Period 1.
  - Sequence 2, Treatment Period 2 (RLZ 12 weeks) using ADA participant category based on RLZ 12 weeks exposure and maximum percent change from Baseline in total IgG in Treatment Period 2.
  - Sequence 1, Treatment Period 1 and Treatment Period 2 (RLZ 24 weeks) using ADA participant category based on RLZ 24 weeks exposure and maximum percent change from Baseline in total IgG in Treatment Period 2

- Sequence 1 Treatment Period 1 and Sequence 2, Treatment Period 2 (RLZ 12 weeks) using ADA participant category based on RLZ 12 weeks exposure and maximum percent change from Baseline in total IgG in Treatment Period 1 for Sequence 1, and Treatment Period 2 for Sequence 2.
- Summary table of mean change from Baseline in BPI-SF Interference score in Treatment Periods 1 and 2, summarized by ADA participant categories (1-6) for the following:
  - Sequence 1, Treatment Period 1 (RLZ 12 weeks) using ADA participant category based on RLZ 12 weeks exposure and change from Baseline in BPI-SF interference score at Visit 15.
  - Sequence 2, Treatment Period 2 (RLZ 12 weeks) using ADA participant category based on RLZ 12 weeks exposure and change from Baseline in BPI-SF interference score at Visit 27.
  - Sequence 1, Treatment Period 1 and Treatment Period 2 (RLZ 24 weeks) using ADA participant category based on RLZ 24 weeks exposure and change from Baseline in BPI-SF interference score at Visit 27.
  - Sequence 1 Treatment Period 1 and Sequence 2, Treatment Period 2 (RLZ 12 weeks) using ADA participant category based on RLZ 12 weeks exposure and change from Baseline in BPI-SF interference score at Visit 15 for Sequence 1, and Visit 27 for Sequence 2.
- Overall summary table of TEAEs summarized by ADA participant categories 1, 5, 6, and 7 where the participant category is based on ADA data for the entire study duration. This table will include the following:

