**Table 5-8: Efficacy endpoint time points**

Endpoint	Baseline measurement	Effect measurement for period 1	Effect measurement for period 2
BPI-SF interference (and other endpoints derived from BPI-SF)	start of Treatment Period 1 Visit 3, D1 pre-dose	pre-dose start of Treatment Period 2 Visit 15, Week 13, D85 (12 weeks of treatment)	Run-Out visit 1 Visit 27, Week 25, D169 (12 weeks of treatment)
Pain and fatigue assessment (NRS)	Run-In visit 2 (starting at D-7 and going to D-1)	Visit 14, Week 12 starting at D78 and going to D84 (12 weeks of treatment)	Visit 26, Week 24 starting at D162 and going to D168 (12 weeks of treatment)
FIQR (and endpoints derived from the FIQR)	Run-In visit 2 Visit 2, D-7	Visit 13, Week 11, D71 (10 weeks of treatment)	Visit 25, Week 23, D155 (10 weeks of treatment)

- BPI-SF interference score is calculated as the mean of the seven pain interference items of the BPI-SF questionnaire. The BPI-SF interference score will be calculated if more than 50% of the total items have been completed on a given administration. For more details on BPI-SF see (Cleeland and Ryan, 1991).

- The FIQR is scored in 3 steps:
  - Step 1. Sum the scores of the items within each of the three domains (domain 1: activities, domain 2: overall impact, and domain 3: symptoms).
  - Step 2. Divide domain 1 score by three, domain 2 score is unchanged, and divide domain 3 score by two. (So if the scores in domains 1, 2 and 3 are 60, 9 and 40, respectively, then domain 1 score divided by three = 20; domain 2 remains unchanged at = 9; domain 3 score divided by two = 20)
  - Step 3. Add the three resulting domain scores to obtain the total Revised Fibromyalgia Impact Questionnaire (FIQR) score. In the example above the total FIQR score would be  $20+9+20 = 49$
  - Missing answers: For unanswered questions the following “weighting” factor should be used. If only  $x$  questions from the first section (function) were answered, one would weigh the summated score of the  $x$  questions by  $9/x$  (as there are 9 items in the function set of questions) Likewise the second section (overall impact) would have a weighting of  $2/x$  (there are only 2 items) and the third section (symptoms) would have a weighting of  $10/x$  (there are 10 items).

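### Outputs labelled RLZ 12 weeks combine Sequence 2's 24-week BPI-SF change, half of it on placebo, with Sequence 1's 12-week change

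*SAP*

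**What the plan says.** - **BPI-SF Baseline.** SAP Table 5-8 sets it at "start of Treatment Period 1 Visit 3, D1 pre-dose" and uses it for the effect measurement in both periods. Table 5-2 agrees, with Screening as the fallback if Day 1 is missing. No Period 2 Baseline is defined for efficacy.
- **Sequence 2 treatment.** SAP Table 5-4: "Sequence 2: Placebo in Treatment Period 1, rozanolixizumab 12 weeks in Treatment Period 2". The first active dose is at Visit 15 (Day 85).
- **ADA Baseline.** SAP Table 5-2: "For participants randomized to Sequence 2, Baseline is the Day 85 (Visit 15, Week 13) pre-dose assessment". SAP 5.7 runs the 12-week ADA classification for Sequence 2 from Visit 15 to Visit 27.
- **ADA by BPI-SF table (SAP 5.7).** There is a row for each sequence. The Sequence 2 row, read at Visit 27, is defined as "Sequence 2, Treatment Period 2 (RLZ 12 weeks) using ADA participant category based on RLZ 12 weeks exposure and change from Baseline in BPI-SF interference". A further row pools "change from Baseline in BPI-SF interference score at Visit 15 for Sequence 1, and Visit 27 for Sequence 2".
- **IgG correlations (SAP 5.5.2).** Total IgG change is plotted against "Change from Baseline at Visit 15 and Visit 27 in BPI-SF interference", with regression lines and Pearson coefficients, by treatment group. SAP Table 5-3 puts Sequence 1 Period 1 and Sequence 2 Period 2 together in the RLZ 12 weeks group. IgG Baseline is Visit 3 for every sequence (Table 5-2).

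**The concern.** A reader will take RLZ 12 weeks to mean symptom change over 12 weeks of rozanolixizumab. For Sequence 2 it is a 24-week change that begins with 12 weeks on placebo, and nothing in either section says so. In the ADA table, one row then uses two reference visits for the same person: Visit 15 for ADA status and Visit 3 for symptoms. An ADA response to a drug not yet given cannot affect the placebo part of that change.

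These outputs are the planned look at whether ADA weakens the effect and whether IgG lowering tracks symptom change, which is the mechanism the study sets out to test. Unlike the primary model, they have no period term to absorb drift.

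**Working it through.** The plan gives no figure to reproduce here. The check concerns windows and what each change contains.

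**1. Windows** (visit days from the protocol Schedule of Activities: Visit 3 = Day 1, Visit 15 = Day 85, Visit 27 = Day 169)

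| Quantity | From - to | Days | Placebo | Active |
|---|---|---|---|---|
| Sequence 1 BPI-SF change | Visit 3 - Visit 15 | 85 - 1 = 84 | 0 | 84 |
| Sequence 2 BPI-SF change | Visit 3 - Visit 27 | 169 - 1 = 168 | 85 - 1 = 84 | 169 - 85 = 84 |
| Sequence 2 ADA category | Visit 15 - Visit 27 | 169 - 85 = 84 | 0 | 84 |

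The Visit 3 reading is not open to doubt. SAP 5.7 also plots Sequence 2's mean BPI-SF change from Baseline at Visits 7, 11 and 15, which a Visit 15 Baseline would not allow.

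**2. What each change contains.** Let p1 and p2 be the non-drug mean changes in Periods 1 and 2, and d the 12-week drug effect. Assume they add and are the same in both sequences.

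- Sequence 1, Visit 3 to 15: p1 + d
- Sequence 2, Visit 3 to 27: p1 + p2 + d
- Sequence 2, Visit 15 to 27: p2 + d

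The gap (Sequence 2 minus Sequence 1) is p2 on the Visit 3 base. If only Sequence 2 is re-based to Visit 15, its size is that of p1 - p2. With equal sequence sizes, the gap moves the pooled mean from Sequence 1's value by p2/2 on the Visit 3 base.

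**3. Illustration.** Take d = -1.0, the size of the planning difference in SAP 3. The documents give no placebo change in BPI-SF, so p1 and p2 are assumptions. The share is p1/(p1 + p2 + d).

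| p1 | p2 | Seq 1 | Seq 2, Visit 3 base | Seq 2, Visit 15 base | Gap, Visit 3 base | Gap, Visit 15 base | Share of Seq 2 change before first active dose |
|---|---|---|---|---|---|---|---|
| -0.5 | 0 | -1.5 | -1.5 | -1.0 | 0 | 0.5 | 33% |
| -0.5 | -0.25 | -1.5 | -1.75 | -1.25 | -0.25 | 0.25 | 29% |
| -1.0 | 0 | -2.0 | -2.0 | -1.0 | 0 | 1.0 | 50% |
| -1.0 | -0.25 | -2.0 | -2.25 | -1.25 | -0.25 | 0.75 | 44% |
| -1.5 | 0 | -2.5 | -2.5 | -1.0 | 0 | 1.5 | 60% |
| -1.5 | -0.25 | -2.5 | -2.75 | -1.25 | -0.25 | 1.25 | 55% |

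A large part of Sequence 2's labelled change can thus arise before any active dose. The mismatch created by pooling is still only p2.

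**4. Effect on the questions asked.** Within the Sequence 2 row, p1 comes before any active dose. It shifts all ADA categories about equally in expectation and mainly adds noise to their contrast. In the pooled row, drift enters a contrast between two categories as p2 times the difference in their Sequence 2 fractions. That is at most the size of p2, or 0.25 points under the assumptions above. In the correlations, IgG and BPI-SF are both measured from Visit 3, so each point is internally consistent. The fault there is one line and one coefficient fitted across two window lengths and two sequences.

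**The case against.** **Both sequences carry placebo response.** A reader might infer that the Sequence 2 row overstates the drug change by p1, the pooled row by p1/2, and that re-basing Sequence 2 to Visit 15 cures this. The documents do not support that. Sequence 1's change is also uncontrolled change from Visit 3 and contains the same p1. If placebo response comes early, p2 is near zero, the SAP's Visit 3 choice aligns the two sequences, and re-basing one of them separates them by p1. This objection stands and limits the point to the mixing of windows.

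**The sequences are already shown separately.** This is true of the ADA table, where the pooled row is an addition. It is not true of the correlations, which SAP 5.5.2 presents by treatment group. Protocol 9.2 also plans participant-level Period 2 minus Period 1 differences by sequence for continuous variables, but not by ADA category.

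**Endpoint-specific Baselines are deliberate.** SAP 5.1.1.3 says so, and each ADA-table row names its visit. Having two Baselines is therefore not a contradiction. The RLZ 12 weeks label still does not tell the reader that Sequence 2's symptom change spans 24 weeks.

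**The consequence is small.** ADA and PD objectives are exploratory, SAP 2 plans no formal hypothesis testing, and these outputs are descriptive. This stands.

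**Conclusion.** The point holds as one of labelling and pooling in exploratory outputs. In the ADA by BPI-SF table and the IgG/BPI-SF correlations, RLZ 12 weeks joins an 84-day change with a 168-day change whose first 84 days are on placebo. In the ADA table, the ADA category also covers only the second half of that window.

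The pooled sequences differ by p2: 0 to 0.25 points for an assumed p2 of 0 to -0.25, with additive effects common to both sequences. For an assumed p1 of -0.5 to -1.5 and d of -1.0, 29% to 60% of Sequence 2's change would precede the first active dose.

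Two stronger inferences fail. The ADA Baseline mismatch does not extend to the IgG correlations, where ADA plays no part. The primary analysis is not compromised either: its mixed model uses Visit 3 as a covariate and has period and period-by-assessment terms. The weight is low.

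**What to change.** - **SAP 5.5.2.** Within RLZ 12 weeks, produce the IgG/BPI-SF scatterplots, regression lines and Pearson coefficients separately by sequence, or adjust for sequence. Either removes the mean gap between sequences whatever p1 and p2 are.
- **SAP 5.7, ADA by BPI-SF table.** Rely on the separate sequence rows already planned. Drop the pooled BPI-SF row, or footnote that it mixes 12-week and 24-week changes. Beside Sequence 2's Visit 3-based change, add a labelled change from Visit 15 pre-dose to Visit 27. Do not put the Visit 15-based change into a pooled row in place of the Visit 3 one.
- **Primary model.** Keep Visit 3 as Baseline.

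The cost is one derived variable and some wording. Splitting leaves at most 20 planned participants per correlation instead of 20 + 20 = 40. On Fisher's z scale the standard error rises from 1/√(40 - 3) = 0.16 to 1/√(20 - 3) = 0.24; adjusting for sequence avoids most of that loss. Sequence 2 participants without a Visit 15 score drop out of the added row.

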## **5.8 Efficacy Analysis**

The observed result and change from Baseline of each efficacy assessment (including the individual items as well as the summary scores) will be tabulated by planned treatment sequence and visit (including Screening and Run-In, if applicable), based on the FAS.

The observed result and change from Baseline of each efficacy assessment (including the individual items as well as the summary scores) will also be summarized by treatment group, based on the FAS.

Mean change from Baseline (with 95% confidence intervals based on summary statistics) for BPI-SF and FIQR will be summarized by treatment sequence and period using a Forest plot. The BPI-SF plot will contain all BPI-SF interference questions as well as the BPI-SF interference score. The FIQR plot will include all individual questions as well as the domain scores and overall FIQR score. Plots will be based on the mean change from Baseline at Assessment 3 in each treatment period.

Figures for mean change from Baseline over time will be generated for each efficacy parameter by treatment sequence over both Treatment Periods, and by treatment and period day. For the latter all combinations of treatment and sequence will be displayed separately (6 symbols per plot) and the periods will be superimposed.

For the NRS measurement collected over multiple days, the average of the measurements related to a given visit will be summarized in the tables and figures, rather than the individual measurements. If two or more pain or fatigue NRS results are recorded on the same calendar day, the latest result of the day will be used for the purpose of calculating the average score, and for display in the summaries. All measurements will be presented in the listings and duplicate scores will be indicated as appropriate.

### 5.8.1 Derivations of Efficacy Variables(s)

The different efficacy variables will have different Baseline and endpoint measurement time points, depending on when the relevant data is being collected. [Table 5-8](#) gives details on the timing of these baseline and effect measurements.

**Table 5-8: Efficacy endpoint time points**

Endpoint	Baseline measurement	Effect measurement for period 1	Effect measurement for period 2
BPI-SF interference (and other endpoints derived from BPI-SF)	start of Treatment Period 1 Visit 3, D1 pre-dose	pre-dose start of Treatment Period 2 Visit 15, Week 13, D85 (12 weeks of treatment)	Run-Out visit 1 Visit 27, Week 25, D169 (12 weeks of treatment)
Pain and fatigue assessment (NRS)	Run-In visit 2 (starting at D-7 and going to D-1)	Visit 14, Week 12 starting at D78 and going to D84 (12 weeks of treatment)	Visit 26, Week 24 starting at D162 and going to D168 (12 weeks of treatment)
FIQR (and endpoints derived from the FIQR)	Run-In visit 2 Visit 2, D-7	Visit 13, Week 11, D71 (10 weeks of treatment)	Visit 25, Week 23, D155 (10 weeks of treatment)

- BPI-SF interference score is calculated as the mean of the seven pain interference items of the BPI-SF questionnaire. The BPI-SF interference score will be calculated if more than 50% of the total items have been completed on a given administration. For more details on BPI-SF see (Cleeland and Ryan, 1991).

- The FIQR is scored in 3 steps:
  - Step 1. Sum the scores of the items within each of the three domains (domain 1: activities, domain 2: overall impact, and domain 3: symptoms).
  - Step 2. Divide domain 1 score by three, domain 2 score is unchanged, and divide domain 3 score by two. (So if the scores in domains 1, 2 and 3 are 60, 9 and 40, respectively, then domain 1 score divided by three = 20; domain 2 remains unchanged at = 9; domain 3 score divided by two = 20)
  - Step 3. Add the three resulting domain scores to obtain the total Revised Fibromyalgia Impact Questionnaire (FIQR) score. In the example above the total FIQR score would be  $20+9+20 = 49$
  - Missing answers: For unanswered questions the following “weighting” factor should be used. If only  $x$  questions from the first section (function) were answered, one would weigh the summated score of the  $x$  questions by  $9/x$  (as there are 9 items in the function set of questions) Likewise the second section (overall impact) would have a weighting of  $2/x$  (there are only 2 items) and the third section (symptoms) would have a weighting of  $10/x$  (there are 10 items).

## 5.8.2 Primary Efficacy Variable

The primary efficacy endpoint is the average BPI-SF interference score after 12 weeks of double-blind treatment, adjusted for Baseline score.

For the purpose of analysis, there will be three treatment groups: placebo, rozanolixizumab for up to 12 weeks [Sequence 1, Period 1 and Sequence 2, Period 2], or rozanolixizumab given beyond 12 weeks [Sequence 1, Period 2]. The main difference of interest is that between rozanolixizumab for up to 12 weeks and placebo.

In order to estimate the mean difference in the average BPI-SF interference scores after 12 weeks of treatment, the BPI-SF interference scores measured at Visits 7, 11, 15, 19, 23, and 27 will be modelled using a longitudinal linear mixed effect model (LMM). The pre-dose value taken at the first visit of Treatment Period 2 (Visit 15) will be used as the measure of treatment effect after 12 weeks of treatment for Period 1, while the pre-dose value taken at Run-Out Visit 27 will be used as the measure of treatment effect after 12 weeks of treatment for Period 2. Any BPI-SF assessments which are not completed within the protocol defined window of the scheduled visit will not be included within the primary efficacy analysis.

